8.2.2.1. Pharmacokinetic Samples

At the visits and times specified in the Pharmacokinetic Sampling, ECG and Immunogenicity Sampling Schedule ([Attachment 4](#)), blood samples of approximately 3 mL each will be collected to determine the serum concentrations of olaratumab. In Part A, blood samples of approximately 3 mL each will also be collected to determine the plasma concentrations of doxorubicin. A maximum of 5 samples may be collected at additional time points during the study if warranted and agreed upon between both the investigator and Lilly. Instructions for the collection and handling of blood samples will be provided by the sponsor. The actual date and time (24-hour clock time) of each sampling will be recorded.

These samples will be analyzed at a laboratory designated by the sponsor. Serum concentrations of olaratumab will be assayed using a validated enzyme-linked immunosorbent assay method. Plasma concentrations of doxorubicin will be assayed using a validated liquid chromatography with tandem mass spectrometry method.

The PK samples will be stored at a facility designated by the sponsor.

The remaining plasma/serum from the samples collected for PK may be pooled and used for exploratory metabolism work as deemed appropriate.

Bioanalytical samples collected to measure investigational product concentration will be retained for a maximum of 1 years following last patient visit for the study.

When enough data for the analysis of the primary and the secondary endpoints has been collected as determined by the sponsor and the patient has continued the study treatment for more than 3 years, PK samples will no longer be collected except for sampling required for the follow-up visit ([Attachment 4](#)).

8.2.3. Samples for Immunogenicity Research

Blood samples of approximately 4 mL for immunogenicity testing will be collected to determine antibody production against olaratumab. A schedule for immunogenicity sample collection is provided in [Attachment 4](#). In addition to the scheduled immunogenicity sampling, in the event of an infusion-related reaction samples are to be collected as close to the onset of the event as possible, at the resolution of the event, and 28 days following the event. An immunogenicity sample should also be collected approximately 28 days after the discontinuation of treatment (ie, 28-day follow-up visit).

Immunogenicity will be assessed by a validated assay designed to detect ADA in the presence of olaratumab. Antibodies may be further characterized and/or evaluated for their ability to neutralize the activity of olaratumab.

Detailed instructions for collecting, processing, storing, and shipping the samples will be provided by the sponsor in a separate procedural manual.

Samples may be stored for a maximum of 15 years following last patient visit for the trial at a facility selected by the sponsor to enable further analysis of immune responses to olaratumab. The duration allows the sponsor to respond to regulatory requests related to olaratumab.

When enough data for the analysis of the primary and the secondary endpoints has been collected as determined by the sponsor and the patient has continued the study treatment for more than 3 years, immunogenicity samples will no longer be collected except for sampling required for the follow-up visit or in the event of an infusion-related reaction ([Attachment 4](#)).

8.2.4. Samples for Translational Research

Exploratory analyses will assess the potentially relevant biomarkers obtained from blood samples. Tumor tissue submission is optional and tumor specimens might be used if available.

- Blood samples and tumor tissues (if available) will be used for the analysis of potential biomarkers related to the mechanism of olaratumab, the PDGF signaling pathway, and the pathobiology of cancer.

Gene expression profiling and/or genetic analyses will not be conducted in any samples collected in this study.

Required samples for biomarker to be collected from all patients in this study are the following:

- plasma samples from whole blood (see Section [8.2.4.1](#))

Optional samples for biomarker research that should be collected from patients in the study where possible are the following:

- archived tumor tissue (see Section 8.2.4.2)

Samples will be collected at the times specified in [Attachment 1](#).

The translational research samples will be coded with the patient number and stored for up to a maximum 15 years after the last patient visit for the study at a facility selected by the sponsor or designee. The samples and any data generated from them can only be linked back to the patient by investigator site personnel. The duration allows the sponsor to respond to regulatory requests related to the study treatment.

Patients will not receive results of these investigations except where required by local law. Samples will be destroyed according to a process consistent with local regulation.

Supplies required for the collection and shipment of the patients' stored samples will be supplied by the central laboratory vendor. Sample handling and shipment to the central laboratory will occur per instructions provided to the study site.

8.2.4.1. Blood Sample for Plasma Collection

Circulating markers may include, but are not limited to, markers relevant to the mechanism of olaratumab, the PDGF signaling pathway, and the pathobiology of cancer.

8.2.4.2. Optional Tumor Tissue Samples

Collection of tumor tissue samples (blocks or slides) is optional for participation in this study. If provided, due diligence should be used to make sure that tumor specimen (not a normal adjacent or a tumor margin sample) is provided. Pathology notes accompanying archival tissue may also be requested. If paraffin-embedded whole blocks will be submitted, the whole blocks will be sectioned. After testing has been completed, the paraffin-embedded whole blocks will be returned to the site. Whole blocks can be returned sooner, if requested by the sites. Partial blocks and slides will not be returned.

Immunohistochemistry may be performed on these tissue samples to assess potential associations with biomarkers relevant to pathways associated with the mechanism of olaratumab, the PDGF signaling pathway, and the pathobiology of cancer and cancer-related conditions, and may also be used for related research methods and clinical outcomes. Additional exploratory markers studied may include, but are not limited to, markers relevant to the PDGF pathway.

8.3. Efficacy Evaluations

A secondary objective of the study is to document any antitumor activity. Refer to [Attachment 1](#) for details regarding the timing of specific efficacy measures.

Each patient will be assessed by one or more of the following radiologic tests for tumor measurement:

- Computed tomography scan
- Magnetic resonance imaging

Each patient's full extent of disease will also be assessed with:

- Tumor measurement by RECIST version 1.1 (Eisenhauer et al. 2009)
- Evaluation of PS

To confirm objective responses, all lesions should be radiologically assessed, and the same radiologic method used for the initial response determination should be repeated at least 4 weeks following the initial observation of an objective response. If a patient is discontinued from the study, repeat radiology assessments may be omitted if clear clinical signs of progressive disease are present.

8.4. Procedure/Sampling Compliance

Every attempt will be made to enroll patients who have the ability to understand and comply with instructions. Noncompliant patients may be discontinued from the study.

The collection times of safety assessments, PK samples, and efficacy measurements are given as targets, to be achieved within reasonable limits. The scheduled time points may be subject to minor alterations; however, the actual collection time must be correctly recorded on the CRF or lab requisition form.

The scheduled collection times may be modified by the sponsor based on analysis of the safety and PK information obtained during the study. Any major modifications that might affect the conduct of the study, patient safety, and/or data integrity will be detailed in a protocol amendment.

9. Data Management Methods

9.1. Data Quality Assurance

To ensure accurate, complete, and reliable data, Lilly or its representatives will do the following:

- provide instructional material to the study sites, as appropriate
- sponsor start-up training to instruct the investigators and study coordinators. This session will give instruction on the protocol, the completion of the CRFs, and study procedures
- make periodic visits to the study site
- be available for consultation and stay in contact with the study site personnel by mail, telephone, and/or fax
- review and evaluate CRF data and/or use standard computer edits to detect errors in data collection.
- conduct a quality review of the database.

In addition, Lilly or its representatives will periodically check a sample of the patient data recorded against source documents at the study site. The study may be audited by Lilly or its representatives and/or regulatory agencies at any time. Investigators will be given notice before an audit occurs.

To ensure the safety of participants in the study, and to ensure accurate, complete, and reliable data, the investigator will keep records of laboratory tests, clinical notes, and patient medical records in the patient files as original source documents for the study. If requested, the investigator will provide the sponsor, applicable regulatory agencies, and applicable ERBs/IRB with direct access to the original source documents.

9.2. Data Capture Systems

9.2.1. Case Report Form

An electronic data capture system will be used in this study. The site maintains a separate source for the data entered by the site into the sponsor-provided electronic data capture system.

For data handled by a data management third-party organization (TPO), eCRF data and some or all data that are related will be managed and stored electronically in the TPO system.

Subsequent to the final database lock, validated data will be transferred to the sponsor.

For data handled by the sponsor internally, eCRF data and some or all data that are related will be managed by the sponsor and stored electronically in the sponsor's system.

9.2.2. Ancillary Data

Data managed by a central vendor will be stored electronically in the central laboratory's database system. Data will subsequently be transferred from the central vendor to the Lilly generic labs system and/or the TPO system.

Bioanalytical data will be stored electronically in the bioanalytical laboratory's database. Data will subsequently be transferred from the bioanalytical laboratory to the Lilly generic labs system and/or the TPO system.

Electrocardiogram data will be stored electronically in the central database system of Lilly's central review organization. Data will subsequently be transferred from the central review organization system to the Lilly generic labs system and/or the TPO system.

When enough data for the analysis of the primary and the secondary endpoints has been collected as determined by the sponsor and the patient has continued the study treatment for more than 3 years, electrocardiogram data will no longer be stored electronically in the central vendor's system.

Data from complaint forms submitted to Lilly will be encoded and stored in the global product complaint management system.

10. Data Analyses

10.1. General Considerations

The study design requires 6 patients at each cohort in Part A for assessing the DLTs observed. This sample size was not based on a statistical power calculation.

In Part B, 6 patients are needed to evaluate PK and safety profile of olaratumab monotherapy. This sample size was estimated empirically based on other Phase 1 oncology studies. The estimation precision of PK parameters in this study is expected to be similar to that in previous studies (Study JGDC and Study JGDF), although there are no inter-subject variability data on a new assay.

Statistical analysis of this study will be the responsibility of the sponsor.

The interpretation of the study results will be the responsibility of the investigator with the sponsor's CRP, pharmacokineticist, and statistician. The CRP and statistician will also be responsible for the appropriate conduct of an internal review for both the final study report and any study-related material to be authorized by Lilly for publication.

Any change to the data analysis methods described in the protocol will require an amendment ONLY if it changes a principal feature of the protocol. Any other change to the data analysis methods described in the protocol, and the justification for making the change, will be described in the clinical study report. Additional exploratory analyses of the data will be conducted as deemed appropriate.

Detailed information regarding the planned statistical analyses will be described in the Statistical Analysis Plan.

10.2. Patient Disposition

The analysis populations are defined as follows:

- Enrolled Population: Anyone who signed the informed consent and who was confirmed to be eligible and have been assigned to a treatment will be included in this population.
- FAS Population: All enrolled patients who received any amount of study drugs (either olaratumab or doxorubicin) will be included in the FAS Population. The FAS Population is based on the intent-to-treat principle and will be used for the analysis of baseline characteristics, efficacy data, safety data, and biomarkers.
- DLT Population: All enrolled patients who will complete Cycle 1 (initial 21-day treatment period), or who will discontinue due to DLT during Cycle 1, will be included in the DLT Population. Patients who will discontinue during Cycle 1 due to other reasons than DLT will be excluded from the DLT Population. The DLT Population will be used for summarizing a proportion of patients with DLT.

Number (percent) of patients in the Enrolled Population, the FAS Population, or the DLT Population (Part A only) will be summarized by part and cohort.

All patient discontinuations will be documented, and the extent of each patient's participation in the study will be reported. If known, a reason for patient discontinuation will be given.

Number (percent) of patients who discontinued will also be summarized by part and reason for discontinuation and by part and cohort.

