7.2.1.3. Dose-Limiting Toxicity Determination (Part A)

Dose-limiting toxicity is defined as an AE during Cycle 1 (first 21 days from Day 1 in Cycle 1) that is possibly related to the study drug(s) (olaratumab and/or doxorubicin) and fulfills any one of the following criteria using the National Cancer Institute (NCI) Common Terminology Criteria for Adverse Events (CTCAE) (v4.03):

- CTCAE Grade 3 or above nonhematologic toxicity. Exceptions will be made for:
 - Nausea, vomiting, diarrhea, constipation, or electrolyte abnormality that can be controlled with treatment.
 - Fatigue and anorexia.
 - Transient (ie, ≤ 1 week) Grade 3 elevations of ALT and/or AST without evidence of other hepatic injury.
- Febrile neutropenia.
- Grade 4 anemia.
- Grade 4 neutropenia lasting >1 week.
- Grade 4 thrombocytopenia, or Grade 3 thrombocytopenia requiring platelet transfusion.
- Toxicities which require dose reduction or omission of study drug(s) (olaratumab and/or doxorubicin) during Cycle 1.
- Any other significant toxicity deemed by the primary investigator and Lilly CRP/clinical research scientist (CRS) to be dose limiting (eg, any toxicity that is possibly related to the study medication that requires the discontinuation of the patient from the study during Cycle 1).

In the event of a Grade 3 or 4 infusion-related reaction, the patient will be replaced; however, the event will not be considered a DLT. An evaluable patient for DLT is defined as a patient who takes 100% of planned dose in Cycle 1 or a patient who experiences DLT in Cycle 1. If a patient is judged to be non-evaluable for DLT, the patient will be replaced by a new patient.

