7.2.2. Dose Adjustments and Delays

7.2.2.1. Delays and Omission

In the case that olaratumab or doxorubicin cannot be administered due to any reason including toxicity, the administration can be delayed beyond the time window within the cycle. If the planned administration cannot be conducted within the cycle, the dose is defined as an omission. For olaratumab-related toxicity \geq Grade 3 not adequately controlled with appropriate supportive care, olaratumab should not be administered until the toxicity becomes \leq Grade 2 or returns to pretreatment baseline.

Part A

Illustrative examples of dose adjustments are shown in [Attachment 5](#).

In general, discontinuation of 1 study drug (olaratumab or doxorubicin) will not necessitate discontinuation of the other study drug. Dose omission, delays, or discontinuation of olaratumab due to an olaratumab-related toxicity will not alter those of doxorubicin. Similarly, olaratumab therapy should not be altered for doxorubicin-related toxicity.

Day 1 of Cycles 2 through 7 (the first cycle of olaratumab monotherapy for the patients who receive doxorubicin on Cycle 7 or later, by reason that cumulative dose of doxorubicin does not reach 500 mg/m² during the first 6 cycles) is defined as the 21st day after the first doxorubicin administration in the previous cycle. Day 1 of Cycle 8 (the second cycle of olaratumab monotherapy for the patients who receive doxorubicin on Cycle 7 or later, by reason that cumulative dose of doxorubicin does not reach 500 mg/m² during the first 6 cycles) or any of the following cycles is defined as the 21st day after the first olaratumab administration in the previous cycle. In the case that olaratumab is delayed or omitted for any reason (including AEs), administration of doxorubicin will continue according to the original schedule. Dose delay of olaratumab on Day 8 is allowed until 7 days before Day 1 of the following cycle. Upon

resolution of the event(s) causing the delay and omission in olaratumab administration, olaratumab treatment will resume according to a Day 1/Day 8 schedule. In this study, every effort will be made to synchronize administration of olaratumab and doxorubicin according to the original dosing schedule; therefore, olaratumab may be administered for up to 4 weeks in a row.

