8.1.2.2.3. Follow-Up Visit

All AEs and SAEs, regardless of relatedness to study drug(s) or protocol procedures, occurring during the follow-up visit must be reported to Lilly or its designee. The follow-up visit starts on the day after the patient and the investigator agree to discontinue the study treatment and extends 28 days (± 5 days) from the last dose of study drug (olaratumab or doxorubicin). For patients who discontinue from the study treatment after a treatment delay, the follow-up visit can be performed after the allowed time window if it is difficult to perform the follow-up procedures within this time period. In such a situation, the follow-up visit should be performed as early as possible. At the end of the follow-up visit, the patient will be required to have specific safety assessments ([Attachment 1](#)).

Following the safety assessments, which mark the end of the follow-up visit, the patient will be discontinued from the study, unless there is an ongoing AE or SAE that is possibly related to study drug. In this instance, the patient should be monitored in subsequent follow-up visits until the event is resolved, the event is no longer considered to be drug-related, the event becomes stable or returns to baseline, a new treatment is initiated for the patient, or the patient dies or is lost to follow-up.

If it is deemed to be in the best interest of the patient to start a new anticancer treatment prior to the scheduled end of the follow-up visit, the follow-up visit duration may be shortened. In this case, the follow-up assessments should be completed prior to the initiation of the new therapy.

After the follow-up visit, AEs are not required to be reported unless the investigator feels the AEs were related to either study drug, drug delivery system, or a protocol procedure. If an investigator becomes aware of SAEs believed to be related to protocol procedures or study drug, the investigator should report the SAE to the sponsor, and the SAE will be entered in the Lilly Safety System.

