8.1.3.4. Infusion-Related Reactions

The NCI-CTCAE definition of infusion-related reactions is provided in [Attachment 8](#).

Symptoms occurring during or following infusion of olaratumab may also be defined according to AE categories such as allergic reaction, anaphylaxis, or cytokine release syndrome. In the setting of symptoms occurring during or following infusion of olaratumab, investigators are encouraged to use the AE term “infusion-related reaction” and any additional terms (including those not listed here) that best describe the event.

Consistent with usual medical practice, selected parenteral medications may be utilized for Grade 2 allergic/hypersensitivity reaction as detailed below. The Lilly CRP or CRS should be contacted immediately if questions arise concerning the grade of the reaction.

The following are treatment guidelines for olaratumab infusion-related reactions:

In general, if a patient experiences a Grade 1 or 2 infusion-related reaction, the infusion should stop and the patient should be treated with an antihistamine (for example diphenhydramine hydrochloride), steroids (for example dexamethasone), acetaminophen, and oxygen (as appropriate), according to standard medical practices. After recovery, the infusion rate should be decreased 50% for the duration of the infusion. After a Grade 1 or 2 infusion reaction, patients should be premedicated with antihistamines, steroids, acetaminophen, etc., as appropriate for subsequent infusions.

A Grade 3 or 4 infusion-related reaction will require immediate treatment, including the use of epinephrine, bronchodilators, and/or glucocorticoids for symptomatic bronchospasm, IV fluids and/or pressors for hypotension, and immediate and permanent discontinuation of olaratumab with appropriate supportive care.

A patient has to be carefully observed for potential infusion-related reactions for approximately 60 minutes after olaratumab administration, especially after the first 2 administrations. If a

patient should have an infusion-related reaction to olaratumab, all attempts should be made to obtain an anti-olaratumab antibody blood sample as close to the onset of the event as possible, at the resolution of the event, and 28 days following the event. In addition, these samples may be assessed for levels of olaratumab (PK assay).

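### The DLT Population that reports Part A's DLT proportion is not the DLT-evaluable set on which each cohort's tolerability is judged

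*Protocol*

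**What the plan says.** **Decision set.** Protocol 7.2.1.3 defines an evaluable patient as "a patient who takes 100% of planned dose in Cycle 1 or a patient who experiences DLT in Cycle 1". It adds: "If a patient is judged to be non-evaluable for DLT, the patient will be replaced by a new patient". It also provides: "In the event of a Grade 3 or 4 infusion-related reaction, the patient will be replaced", and states that the reaction is not a DLT. Protocol 7.2.1.5 applies its rule to evaluable patients. The DLT frequency must be below 33%; 0 or 1 of 6 is tolerable, 2 goes to discussion, and 3 or more is not tolerable.

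**Reporting set.** Protocol 10.2 defines the DLT Population as "All enrolled patients who will complete Cycle 1 (initial 21-day treatment period), or who will discontinue due to DLT during Cycle 1". It then excludes everyone who discontinues in Cycle 1 for a reason other than DLT. SAP 6.1.1 repeats this definition. Protocol 10.4 and SAP 6.11.2 summarize DLTs on this set. The SAP 6.15 interim follows the Cohort 2 DLT evaluation, informs the decision to join Phase 3, and takes its safety analyses from SAP 6.11, so it uses the same set.

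**The concern.** Safety and tolerability is Part A's primary objective, and the DLT proportion is its most direct summary. A reader of the report will assume that the proportion shown is the one on which the cohort was judged. The two definitions differ in kind: one depends on dose received or on any DLT, the other on completing the cycle or on the reason for leaving it. Neither document cross-refers or reconciles them. The most awkward difference is that the reporting set can remove a patient who had a DLT. That lowers the reported rate on the primary objective.

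**Working it through.** **Step 1. The plan's own rule at six patients.** 1/6 = 16.7%, below 33%. 2/6 = 33.3%, not below 33%. 3/6 = 50.0%. The counts and the percentage in 7.2.1.5 therefore agree at the planned size. The planned total also reproduces: 3 cohorts x 6 + 6 in Part B = 24.

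**Step 2. Patients whom the two definitions treat differently.**

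- *DLT, then leaves Cycle 1 for another reason.* Febrile neutropenia, for example, is a DLT under 7.2.1.3 whether or not treatment stops. If that patient then leaves for progression or withdraws consent, 7.2.1.3 counts the patient and 10.2 expressly excludes the patient.
- *Grade 3/4 infusion reaction, doxorubicin continued.* 7.2.1.3 replaces the patient. Protocol 8.1.3.4 requires "immediate and permanent discontinuation of olaratumab with appropriate supportive care", but Protocol 7.2.2.1 says "discontinuation of 1 study drug (olaratumab or doxorubicin) will not necessitate discontinuation of the other study drug". The patient can therefore complete Cycle 1. Because 10.2 does not say whether discontinuing means one drug or both, the patient can stay in as a non-DLT.
- *Dose missed for a non-toxicity reason, cycle completed.* 7.2.1.3 replaces the patient and 10.2 keeps the patient. This type is narrow. A toxicity that requires omission is itself a DLT, and a dose made up within the cycle is only a delay: "If the planned administration cannot be conducted within the cycle, the dose is defined as an omission".
- *Fully dosed, leaves before Day 21 without a DLT.* On schedule, all Cycle 1 doses are given by Day 8. 7.2.1.3 counts the patient because its evaluability wording has no observation condition; 10.2 drops the patient. Here 7.2.1.3 is the weaker text.

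**Step 3. Effect of one such patient.** Let x be the DLT count and n the number evaluable. The reported proportion is (x-1)/(n-1) for a dropped DLT patient, x/(n+1) for a retained replaced patient, and x/(n-1) for a dropped non-DLT patient.

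| Patient type | Judged 2/6 = 33.3% | Judged 1/6 = 16.7% |
|---|---|---|
| DLT, left for another reason | 1/5 = 20.0% | 0/5 = 0% |
| Replaced, but completed Cycle 1 | 2/7 = 28.6% | 1/7 = 14.3% |
| Fully dosed, left early without DLT | 2/5 = 40.0% | 1/5 = 20.0% |

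Two retained replaced patients would give 2/8 = 25.0%. The error can go in either direction.

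**Step 4. Can Day 21 be observed after early discontinuation?** For a patient whose last dose is on Day 8, the follow-up visit falls at 8 + 28 = Day 36, or Day 31 at the early end of the 5-day window. Both are past Day 21. The exception in Protocol 8.1.2.2.3 is that, for new anticancer treatment, "the follow-up visit duration may be shortened".

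**The case against.** The strongest reply is that no decision changes. The 33% criterion belongs to 7.2.1.5 and is applied there to evaluable patients. Neither Protocol 10.4 nor SAP 6.11.2 applies a threshold to the reported proportion, and SAP 6.15 sets no DLT cut-off for joining Phase 3. Moreover, 2/6 is not a failure; it goes to discussion. All of this stands. A reader might infer that a reported 2/7 turns an intolerable dose into a tolerable one, and the documents do not support that.

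A second reply is that the SAP already lists DLTs, exposure, omissions, adverse events and reasons for discontinuation. With about six patients per cohort, a careful reader could rebuild the evaluable set. That is largely true, but the listings do not correct the summary figure, which is the number likely to be quoted.

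Third, the patient types are narrow, the documents give no frequency for any of them, and 7.2.1.5 does state the 21-day window. This limits the size of the problem but does not reconcile the definitions.

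A reader might also infer that 7.2.1.5 contradicts itself when a cohort is expanded after 2 DLTs, because 3/10 = 30.0%, 3/11 = 27.3% and 3/12 = 25.0% fall below 33% while the count rule rejects 3 DLTs. The documents do not support so strong a reading. The third-DLT rule is mandatory, and the 33% sentence can be read as a further condition. At 3/7 = 42.9%, 3/8 = 37.5% and 3/9 = 33.3% the two agree anyway. Expansion to 10 is neither planned nor suggested, since the planned 24 is exactly 4 x 6. What remains is an unstated expansion size, with discretion given to the sponsor and investigators.

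**Conclusion.** The point holds as a mismatch between the set that is reported and the set that is judged. It is a stated rule that can give the wrong proportion for Part A's primary objective, not merely missing detail. One patient of the relevant type moves a cohort judged at 33.3% to a reported 20.0%, 28.6% or 40.0%, and one judged at 16.7% to 0%, 14.3% or 20.0%. These are illustrations at n = 6 with a single affected patient. The 28.6% and 14.3% figures for an infusion-reaction patient also assume that doxorubicin continues and that stopping olaratumab alone is not read as discontinuation under 10.2. How often any of this would happen cannot be estimated from the documents. The tolerability judgment does not depend on the reporting set. The mismatch should be corrected because the correction costs so little.

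**What to change.** Use one DLT-evaluable definition in Protocol 7.2.1.3, Protocol 10.2 and SAP 6.1.1:

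- Include every patient with a DLT in Cycle 1, whatever the reason for discontinuation.
- Include every patient who received all of the planned Cycle 1 dose and was observed through Day 21 without a DLT. Follow-up data may supply the observation for a patient who stopped treatment early.
- Exclude patients replaced for a Grade 3/4 infusion reaction who had no DLT, whether or not doxorubicin continued.

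The cost is wording in three places. The one practical downside is that a fully dosed patient not observed to Day 21, for example because follow-up was cut short for new anticancer treatment, would need replacing.

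As a minor clarification, state in Protocol 7.2.1.5 that 3 DLTs is an absolute cap that applies in addition to the 33% criterion when a cohort is expanded after 2 DLTs. This adds no patients.
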